## 6. OBJECTIVES

The objective of this extension study is to evaluate the long-term safety of treatment with DE-109 (440 µg) in subjects with non-infectious uveitis of the posterior segment of the eye.

## 7. INVESTIGATIONAL PLAN

### 7.1. Overall Study Design and Plan

This is a multicenter, open-label, extension study of intravitreal injections of the 440 µg dose of DE-109 in subjects with non-infectious uveitis of the posterior segment who received any dose of DE-109 and exited the SAKURA program under Santen Protocol 32-007, Amendment 05.

Subjects who were randomized and received at least two injections of DE-109 during the first five months of the SAKURA study and obtained clinical benefit from the study medication, as determined by the Investigator, may be considered for entry in this 12-month extension study. The minimum time lag from last injection in the SAKURA program to entry into the current protocol is 60 days.

The study eye to be treated in this extension study will be the same as the eye treated during the SAKURA program. The study eye must meet all eligibility criteria of the extension study.

DE-109 should NOT be administered to the fellow eye. If the fellow eye requires treatment during the study, alternative local therapies (e.g., intravitreal or periocular injection of triamcinolone acetonide, Ozurdex, Iluvien, anti-VEGF treatments or photodynamic therapy, etc) may be administered to that eye. The regimen and frequency of treatments for the fellow eye will be at the Investigator's discretion.

Study assessments will be conducted for all subjects at Day 1 (Baseline) and Month 12. Each subject will be followed according to the Investigator's standard clinical practice at non-study visits. DE-109 treatment may be administered in the study eye at the Investigator's discretion during the 12-month study period but no more frequently than every 60 days.

If the Investigator administers a DE-109 injection to the subject, the visit will be considered a Post-Baseline PRN Treatment Visit and procedures will be performed and recorded as specified in this protocol (See [Table 3](#)).

All subjects will exit the study at Month 12, unless terminated early. Adverse events (AEs) will be recorded and collected throughout this extension study, up to the Month 12 exit visit.

It is anticipated that approximately 200 subjects from the SAKURA program may be enrolled in this study. Subjects will be screened for eligibility and written informed consent will be obtained before any study related procedures are performed.

#### 7.1.1. Discussion of Study Design

This study is designed to provide access to DE-109 (440 µg) for those subjects who received treatment during the SAKURA program. In addition the study will evaluate the long-term safety of DE-109.

The 440 µg dose of DE-109 will be the only dose utilized in this open-label study. Subjects will be evaluated for treatment with DE-109 as needed, but may not receive an injection of DE-109 more frequently than every 60 days. DE-109 may only be administered to the study eye.

Rescue treatment for the study eye and all treatments for the non-study eye are to be administered at the discretion of the Investigator. The long-term safety of DE-109 (440 µg) will

be assessed based on adverse events (AEs), best-corrected visual acuity (BCVA), intraocular pressure (IOP), indirect ophthalmoscopy variables, VH and the use of rescue therapy.

The final safety data evaluation will be assessed at Month 12. Interim analyses may be performed by the Sponsor at various times during the study.

## **7.2. Number of Subjects**

The number of subjects to be enrolled in the study will be approximately 200 subjects.

## **7.3. Treatment Assignment**

This is an open-label study and all subjects will receive the 440 µg dose of DE-109.

## **7.4. Criteria for Study Termination**

This study may be stopped by Santen at any time following appropriate notification.

## **7.5. Study Procedures**

All subjects must sign a written informed consent form (ICF) before undergoing any study-related procedure. Each subject will be assigned the same patient number assigned to them in the SAKURA program.

A Schedule of Events is provided in [Table 3](#) and detailed procedures for examinations can be found in Section [21.4](#).

**Table 3: Schedule of Events**

	Visit 1 Day 1 Screening/Baseline	Post-Baseline PRN Treatment Visits	Visit 2 Month 12 or Early Termination d
Assessment Window (Days)	-	≥60 days since last injection	±14
Informed Consent a	X		
Demographics	X		
Medical/Surgical history	X		
Medications	X	X	X
Urine pregnancy test, if appropriate	x b	x b	x b
Inclusion/exclusion criteria	X		
Best-Corrected Visual Acuity	X	X	X
Intraocular pressure	x c	x c	X
Indirect ophthalmoscopy e	X	X	X
Vitreous haze	X	X	X
DE-109 administration, if needed	x	X	
Adverse events	x f	x f	X

a. Informed consent will be obtained prior to conducting any study-related activities.

b. Urine pregnancy tests are to be performed on all women of child-bearing potential.

c. On days when DE-109 injections are administered perform IOP before and 40 (±10) minutes after DE-109 injection.

d. For Early Termination Visits please complete the procedures for the Month 12 visit.

e. Indirect ophthalmoscopy will be performed prior to each study drug injection and then again within 30 minutes after study drug injection

f. On days when DE-109 injections are administered AEs will be elicited before and after DE-109 injection.

### 7.5.1. Visit 1 - Day 1 - Screening/Baseline

- Explain the purpose and details of the study to the subject and obtain written informed consent prior to the subject's participation in any extension study related activity.
- Determine if the subject has:
  - A subject number from participation in the SAKURA program, Amendment 05
  - Received at least two treatments of DE-109 in the first five months of the SAKURA program
  - Received clinical benefit from treatment with DE-109 as determined by the Investigator.
- Record subject's demographics, medical and surgical history and medications.
- If the subject is a woman of child-bearing potential, perform a urine pregnancy test.
- Review the inclusion and exclusion criteria. If the subject has met the inclusion/exclusion criteria, the subject may continue in the study.
- Perform the following assessments:

**For subjects exiting the SAKURA program at this visit, the following assessments will be obtained from the SAKURA Termination Visit. Please skip to "Evaluation of Need for Treatment."**

- BCVA
- IOP
- Indirect ophthalmoscopy
- VH.
- **Evaluation of Need for Treatment** - If in the judgment of the investigator, the subject needs DE-109 treatment, it has been at least 60 days since the last treatment, and the results of the urine pregnancy test were negative (for women of child-bearing potential), perform the study drug administration procedures as described in Section [10.4](#) and [10.5](#).
- The following assessments must be performed after the administration of study drug:
  - Indirect ophthalmoscopy within 30 minutes following injection
  - IOP 40 ( $\pm 10$ ) minutes following injection
  - AEs

### 7.5.2. Visit 2 - Month 12 or Early Termination

- At Day 360 ( $\pm 14$ ) or if the subject is exiting the study early, perform the following assessments:
  - Update medications
  - Urine pregnancy test for women of child-bearing potential

- BCVA
- IOP
- Indirect ophthalmoscopy
- VH
- AEs.
- Exit the subject from the study.

### 7.5.3. Post-Baseline PRN Treatment Visit

The subject may receive DE-109 treatments at the discretion of the Investigator, but no more frequently than every 60 days. If a subject receives treatment with DE-109 between scheduled study assessments, the following procedures will be performed:

- Update medications
- If the subject is a woman of child-bearing potential, perform a urine pregnancy test
- BCVA
- IOP
- Indirect ophthalmoscopy
- VH
- AE.
- If in the judgment of the Investigator, the subject needs DE-109 treatment, it has been at least 60 days since the last treatment, and the results of the urine pregnancy test were negative (for women of child-bearing potential), perform the study drug administration procedures as described in Section 10.4 and Section 10.5.
- The following assessments must be performed after the administration of study drug:
  - Indirect ophthalmoscopy within 30 minutes following injection
  - IOP 40 ( $\pm 10$ ) minutes following injection
  - AEs.

## 8. SELECTION AND WITHDRAWAL OF SUBJECTS

Eligible subjects must meet all eligibility criteria described in Section 8.1 and Section 8.2.

### 8.1. Inclusion criteria

At Day 1, a subject from the SAKURA program must meet all of the following inclusion criteria:

1. Have a subject number from participation in the SAKURA program
2. Exited the SAKURA program under Amendment 05
3. Have received at least two injections of DE-109 in the first five months of the SAKURA program
4. Received clinical benefit from treatment with DE-109 as determined by the Investigator
5. Female participants of childbearing potential must not be pregnant or breast-feeding, have a negative pregnancy test at screening and must be willing to undergo pregnancy tests throughout the study
6. Both female participants of childbearing potential and male participants able to father children must have (or have a partner who has) had a hysterectomy or vasectomy, must abstain from intercourse or must agree to practice acceptable methods of contraception throughout the course of the study.
7. Ability to give informed consent and attend all study visits

### 8.2. Exclusion criteria

A subject from the SAKURA program with any of the following conditions if not eligible to participate in the study:

#### Ocular:

1. Active infectious uveitis. However, if the uveitis is the consequence of a previous infectious disease, such as tuberculosis, the previous infectious disease must be confirmed as no longer active.
2. Any implantable corticosteroid-eluting device (e.g. Ozurdex, I-vation, Iluvien, fluocinolone acetonide [FA] intravitreal implant) in the study eye:
  - a. If the Investigator confirms the device has no demonstrable efficacy as indicated in the package insert, the subject will be eligible
  - b. If a Medidur implant, Iluvien or Retisert has been implanted no less than 3 years and 90 days prior to Day 1, the subject will be eligible
  - c. If a Ozurdex implant, has been implanted no less than 180 days prior to Day 1, the subject will be eligible
3. Clinically suspected or confirmed central nervous system or ocular lymphoma
4. Progressive glaucoma which is unresponsive to treatment

5. Intraocular pressure of > 21 mmHg while on medical therapy, or chronic hypotony (<6 mmHg)
6. Any significant ocular disease that could compromise vision in the study eye. These include, but are not limited to:
  - a. Diabetic retinopathy: proliferative diabetic retinopathy (PDR) or non-proliferative diabetic retinopathy (NPDR) that compromise vision. Subjects with NPDR or PDR that does not compromise vision are not excluded from the study;
  - b. Wet age-related macular degeneration;
  - c. Myopic degeneration with active subfoveal choroidal neovascularization
7. Any of the following treatments to the study eye:
  - a. Intravitreal injections in the past 14 days
  - b. Intravitreal injections of DE-109 in the past 60 days
8. Ocular surgery within the past 30 days
9. Ocular or periocular infection in either eye
10. History of herpetic infection in the study eye or adnexa
11. Presence of known active, inactive toxoplasmosis or toxoplasmosis scar in either eye
12. Presence of any form of ocular malignancy in the either eye including choroidal melanoma
13. History of vitrectomy in the study eye

**Non-Ocular:**

14. Allergy or hypersensitivity to study drug product or other study related procedures/medications
15. Participation in other investigational drug (SAKURA is an exception) or device clinical trials within 30 days prior to Day 1, or planning to participate in other investigational drug or device clinical trials for the entire duration of the study. This includes both ocular and non-ocular clinical trials.
16. Any recent systemic infection within 30 days of Day 1
17. Known to be immunocompromised
18. History of or active cytomegalovirus infection or clinical evidence of active cytomegalovirus infection at Day 1
19. History of other disease, metabolic dysfunction, physical examination finding, or clinical laboratory finding giving reasonable suspicion of a disease condition that contraindicates the use of an investigational drug, might affect the interpretation of the results of the study, or renders the subject at high risk for treatment complications

20. Malignancy in remission for less than 5 years prior to study participation (except basal cell or squamous cell skin cancer, or treated melanoma of the skin less than 24 months since last treatment)
21. Females who are pregnant or lactating and females of child-bearing potential who are not using adequate contraceptive precautions (i.e., intrauterine device, oral contraceptives, barrier method, or other contraception deemed adequate by the Investigator)
22. Use of medically prescribed marijuana or other illegal medication
23. Active systemic sarcoidosis within the last 30 months (i.e. subjects with uveitis secondary to sarcoidosis will be eligible as long as systemic sarcoidosis is not active and systemic immunosuppressive therapy has not been given in the last 30 months).
24. Therapeutic radiation to the head or neck within 90 days prior to Day 1 and throughout the study.

In addition, the Investigator or Santen Medical Monitor may declare a subject ineligible for any sound reason.

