16. Any recent systemic infection within 30 days of Day 1
17. Known to be immunocompromised
18. History of cytomegalovirus infection or clinical evidence of active cytomegalovirus infection at Day 1
19. History of other disease, metabolic dysfunction, physical examination finding, or clinical laboratory finding giving reasonable suspicion of a disease condition that contraindicates the use of an investigational drug, might affect the interpretation of the results of the study, or renders the subject at high risk for treatment complications
20. Malignancy in remission for less than 5 years prior to study participation (except basal cell or squamous cell skin cancer, or treated melanoma of the skin less than 24 months since last treatment)
21. Females who are pregnant or lactating and females of child-bearing potential who are not using adequate contraceptive precautions (i.e., intrauterine device, oral contraceptives, barrier method, or other contraception deemed adequate by the Investigator)
22. Use of medically prescribed marijuana or other illegal medication
23. Active systemic sarcoidosis within the last 30 months (i.e. subjects with uveitis secondary to sarcoidosis will be eligible as long as systemic sarcoidosis is not active and systemic immunosuppressive therapy has not been given in the last 30 months)
24. Therapeutic radiation to the head or neck within 90 days prior to Day 1 and throughout the study

In addition, the Investigator or Santen Medical Monitor may declare a subject ineligible for any sound reason.

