## 9. TREATMENT OF SUBJECTS

### 9.1. Description of Study Drug

DE-109 is a depot formulation of sirolimus, an immunomodulatory agent which inhibits the mammalian target of rapamycin (mTOR), a serine/threonine protein kinase that regulates cell growth, proliferation, motility and survival through changes in transcription and protein synthesis.

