#### **18.2.1. Source Documents**

The Investigator must maintain detailed source documents on all study subjects who provide informed consent. Source documents include subject medical records, hospital charts, clinic charts, study files, as well as the results of diagnostic tests (e.g., laboratory tests, visual field test printouts).

The following minimum information should be entered into the subject's medical record:

- The date the subject entered the study and the subject number
- The study protocol number and the name of Santen Inc.
- The date that informed consent was obtained
- Evidence that the subject meets study eligibility requirements (e.g., medical history, study procedures and/or evaluations)
- The dates of all study-related subject visits
- Evidence that required procedures and/or evaluations were completed
- Use of any concomitant medications
- Documentation of study drug accountability
- Occurrence and status of any AEs
- The date the subject exited the study and a notation as to whether the subject completed or terminated early from the study, including the reason for early termination

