## **21.4. Appendix D - Procedures for Examinations**

### **21.4.1. Demographics, Medical History and Medication**

Demographics, medical and surgical history, medications, current ocular and systemic conditions will be obtained through subject interviews at Day 1. Medications will be updated at each visit, as appropriate.

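### Exclusion item 20 is reversed for skin melanoma: treatment within the last 24 months is exempt, while treatment 24 to about 60 months ago is excluded

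*Protocol*

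**What the plan says.** Protocol Section 8.2 opens by stating that a subject with any listed condition cannot take part. Item 20 lists "Malignancy in remission for less than 5 years prior to study participation" and then, in one parenthesis, removes some cases from that bar: "except basal cell or squamous cell skin cancer, or treated melanoma of the skin less than 24 months since last treatment". Item 20 of the synopsis reads the same.

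Three other provisions bear on the point:

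- **Item 12** deals with malignancy of the eye only.
- **Item 19** is a general exclusion. It covers, among other things, a disease history that "renders the subject at high risk for treatment complications".
- **The closing sentence of Section 8.2** adds that the Investigator or Medical Monitor "may declare a subject ineligible for any sound reason".

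Protocol Section 9.1 describes the product: "DE-109 is a depot formulation of sirolimus, an immunomodulatory agent".

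**The concern.** A time limit on a cancer exception would be expected to let in the older, more stable case. This one lets in the most recent. A subject just treated for melanoma passes item 20, a subject three years out fails it, and a subject more than five years out passes again. The documents give no reason for an order of eligible, excluded, eligible.

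The criterion is operative, the drug is immunomodulatory, and the study's only objective is long-term safety. Applied literally, item 20 fails to screen out the melanoma most recently treated and turns away subjects with longer remission.

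**Working it through.** The plan gives no figure to reproduce, so the check is one of logic.

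**Inputs (Section 8.2, item 20).** The look-back is 5 years, or 60 months of remission. The melanoma exception applies under 24 months since last treatment.

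**Notation.** Let *t* be months since last melanoma treatment and *d* the months from last treatment to the start of remission. The documents do not say when remission starts. I take *d* = 0 and vary it from −12 to +12 as an assumption. A subject not yet in remission counts as under 5 years.

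**Rule as written.** Excluded if *t* < 60 + *d* and not *t* < 24. With *d* = 0:

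| Months since last treatment | Excluded by item 20 as written | Excluded if the exception read *at least 24 months* | Excluded if the melanoma exception were deleted |
|---|---|---|---|
| 1, 6, 12, 23 | No | Yes | Yes |
| 24, 36, 48, 59 | Yes | No | Yes |
| 60, 72 | No | No | No |

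**Sensitivity to the start of remission.** The excluded band runs from 24 to 60 + *d*. The last two columns count months within *t* = 0 to <60 where the written rule gives the opposite answer.

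| *d* | Excluded band (months) | Width | Reversed against *at least 24 months* | Reversed against deletion |
|---|---|---|---|---|
| −12 | 24 to <48 | 24 | 24 + 24 = 48 of 60 | 24 of 60 |
| 0 | 24 to <60 | 36 | 24 + 36 = 60 of 60 | 24 of 60 |
| +12 | 24 to <72 | 48 | 24 + 36 = 60 of 60 | 24 of 60 |

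The excluded band vanishes only if 60 + *d* ≤ 24, that is *d* ≤ −36. Even at *d* = −36 the exemption below 24 months differs from either repair in 24 of 60 months.

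**Could the melanoma phrase be an added exclusion?** The rule would then be *t* < 60 or *t* < 24, which reduces to *t* < 60. The 24-month limit would do nothing, and the phrase would have to be detached from the single *except* that governs the parenthesis. It would need correcting on that reading too.

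**Comparison with the rest of the list.** The other time-limited exclusions (items 7, 8, 15, 16, 23 and 24) all bar the recent event. The implant exceptions in items 2b and 2c restore eligibility only after enough time has passed; for one implant, the subject qualifies if it "has been implanted no less than 180 days prior to Day 1, the subject will be eligible". Only the melanoma exception favours recency.

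**The case against.** The strongest case on the other side is that little follows from the error.

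- **Enrolment and analysis.** SAP Section 3.3 says enrolment was completed by 18 November 2016 with 60 subjects. The analysis is descriptive, and the Safety population does not depend on item 20. This stands.
- **Who could reach item 20.** Every candidate had already been in SAKURA, had at least two DE-109 injections in its first five months and was judged to have benefited. SAKURA's own malignancy criteria are not supplied, so the number who could fall in either band cannot be judged. This stands, and it bears on the count, not on the wording.
- **Backstops.** Item 19 and the discretion clause can keep out a recently treated case. That is true, but only by judgement. Neither can admit a subject whom the text bars between 24 and about 60 months, although wrongly barring someone endangers no enrolled subject.
- **Intent.** No passage says the sponsor meant at least 24 months, and the implant items concern implanted steroid devices, not cancer remission. This stands: the reading of the text is firm, but the replacement is an inference.
- **Protocol version.** The SAP applies to US Amendment 01 of 02 June 2016, whose text is not supplied and could differ. However, only 13 of the 60 subjects signed its consent, and SAP Section 8.8 says all subjects under it joined after Day 1. On these documents a correction there would not have governed Day 1 screening. SAP Section 6.3 names sites in the US, India and Europe, and which version applied at each is unknown.
- **Drug risk.** No passage links this intravitreal dose to melanoma. This stands, and no such link is claimed here.

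**Conclusion.** The concern holds for the supplied text. The melanoma exception in item 20 is reversed in both places where it appears, and no other provision corrects it. Counting remission from last treatment, it exempts months 0 to <24 and excludes months 24 to <60. Moving the start of remission by 12 months either way shifts the upper limit to 48 or 72 months and leaves the reversal in place.

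The severity is minor. The month counts describe a timeline, not people; affected subjects are unknown and possibly 0 of 60. No estimate, population or hypothesis depends on the item. Confidence is high that the text is reversed, and lower as to which replacement the sponsor intended.

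**What to change.** In Section 8.2 and the synopsis, replace *less than* with *at least* before the 24 months, subject to confirmation by the sponsor's medical team. The alternative is to delete the melanoma exception so that the 5-year rule applies. The two options differ only from 24 months to the 5-year limit, where the first admits and the second excludes.

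Rewording cannot change who entered, so also check the 60 subjects for prior skin melanoma and its last treatment date. The material should exist: Protocol Section 21.4.1 says that "medical and surgical history, medications, current ocular and systemic conditions will be obtained through subject interviews at Day 1", and Section 18.2.1 requires in the medical record "Evidence that the subject meets study eligibility requirements (e.g., medical history, study procedures and/or evaluations". The tables in SAP Section 7.3, by system organ class and preferred term, carry no time since treatment, so this has to be done subject by subject.

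Note any subject treated less than 24 months before Day 1 beside the adverse event listings of SAP Section 8.1. Do not reclassify protocol deviations: a subject who met the text in force at entry did not deviate from it.

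The cost is one phrase in two places and one history check in at most 60 subjects. No analysis, population or deviation table changes.
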